Protocol Cover Page

Study title: Characterizing Late-season Influenza Vaccine Responses to Compare the 2023 and 2024 Vaccine Formulations

NCT number: NCT06567860

Document date: 2024-07-22

1. Project Title

Characterizing late-season influenza vaccine responses to compare the 2023 and 2024 vaccine formulations

2. Principal Investigator

[name]

3. Summary

Provide a brief overview on the proposed study in lay language (no more than one paragraph).

Every 1-2 years, the seasonal influenza vaccine composition changes to include updated viruses, yet the precise effects of updating the vaccine remain understudied. Since the vaccine formulation for each season (with a season defined as starting in July and ending the following June) expires on June 30, vaccine formulations cannot be compared head-to-head. Thus, the 2023 and 2024 vaccines have only been compared by analyzing people given the former vaccine in the fall of 2023 and people given the latter vaccine in the fall of 2024, and baseline repertoires may have greatly changed over the course of that year. To that end, we intend to vaccinate a small cohort with the 2023 influenza vaccine between May-June 2024, which will let us compare between individuals receiving the 2023 vaccine last fall, the 2023 vaccine late in the season (our cohort), and the 2024 vaccine next fall.

June 2024 Amendment: We will investigate whether the late-season 2023 vaccine primed this cohort to respond better to the standard 2024 vaccine with standard timing (vaccine administered around September-October).

4. Project Personnel

Please utilize the Human Subjects Protocol Personnel Attachment to list all personnel engaged in human subjects research on this project.

Personnel (including offsite collaborators) should be listed if they will:

- be involved with planning and designing the study
- intervene with subjects by performing research procedures
- participate in the recruitment and/or selection of subjects
- participate in the informed consent process
- have access to subject identifiable data

Check to confirm that current Protocol Personnel Attachment is included with this submission

Yes

Please ensure that training certificates are on file with the IRB for all individuals listed.

[CITI "Protecting Human Research Participants" online course](#)

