Aim 3: Determine which factors affect the antibody response post-vaccination. Using vaccine studies from the past decade, we have quantified how various factors (e.g., age, sex, BMI) affect the antibody response. In this study, we are adding two additional factors within our questionnaire – how much do you exercise and how much sleep did you get the night before – that have been demonstrated to affect the vaccine response to influenza and other pathogens [Rayatdoost 2022, *Yale J Biol Med*]. Comparing this cohort to other publicly available vaccine studies, we will quantify the impact of both features in the vaccine response.

June 2024 Amendment

Aim 4: Does administering the 2023 vaccine late in the season prime the subsequent 2024 response? By comparing antibody responses in our cohort versus responses from other influenza vaccine studies (where participants are annually vaccinated), we will quantify whether this prime-boost regime leads to fundamentally stronger or longer-lasting responses.

7. Background and Significance

Provide relevant background information to justify performing the proposed study. Describe any relevant preliminary data. Indicate the significance of the research based on the existing literature and how will it add to existing knowledge.

The unparalleled impact of the ongoing COVID-19 pandemic and the four pandemics caused by influenza viruses over the past century underscore the significant threat respiratory viruses pose to human health. By the end of 2023, COVID-19 had resulted in over 100 million infections in the United States alone (WHO). Similarly, influenza caused ~26 million infections in 2022-23 and ~45 million infections in 2023-24 thus far (CDC). One of the major challenges we face, if we wish to successfully combat a future pandemic, is the establishment of strong and durable immune memory against these viral threats. Currently, both SARS2 and influenza viruses evade vaccine induced responses and must be regularly reformulated to generate protective immunity, yet the repercussions of the many choices that must be made during vaccine selection, especially the choice of the vaccine's composition, remain poorly understood. Quantifying the differences between individuals receiving the 2023 and 2024 vaccines as close together in time as possible will clarify the effect of changing the vaccine.

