The [name] lab has developed a unique framework to use baseline (day 0) antibody inhibition profiles to predict the subsequent response at day 28 and day 90 post-vaccination. Our models are trained using prior vaccine studies to predict the outcomes of future responses. We have demonstrated our predictive power on influenza vaccine data from every season from 2014-15 to 2023-24 and used these methods to quantify the different effects from each year's vaccine. For example, we found that the 2023 vaccine elicited ~2x lower fold-change in H3N2 serum hemagglutination

compared to the 2022 vaccine (even though both contained the same H3N2 vaccine strain), demonstrating that the immune background can substantially affect the vaccine response.

Using this cohort, we will quantify the vaccine responses between: (1) previous vaccine studies administered last fall using the 2023 vaccine, (2) our late-season study administering the 2023 vaccine, and (3) future vaccine studies next fall administering the 2024 vaccine. In each case, we will analyze the peak vaccine response (at day 28) and its durability (by assessing vaccine waning at day 90) as well as quantify how accurately each vaccine cohort can predict the other cohorts to disentangle the effects of exposure background and vaccine composition. In doing so, we will demonstrate a means to rigorously assess vaccine responses across seasons without the confounding effects of different immune backgrounds.

June 2024 Amendment: Using the cohort from this study, we will quantify the vaccine responses of people receiving the influenza 2024 vaccine whose previous vaccine was either administered: (1) in May/June [our late-season vaccine study] or (2) in the Fall of 2023 [using other annual vaccine studies]. In each case, we will analyze the peak vaccine response (at day 28) and its durability (by assessing vaccine waning at day 90) as well as quantify how accurately each vaccine cohort can predict the other cohorts. Our goal will be to demonstrate whether such late-season vaccine administration can boost subsequent vaccine responses.

8. Estimated Duration of the Project

State the duration of the entire study from opening of study for participant recruitment through end of follow up and data analysis to project completion.

We estimate the study will take 10 years starting in 2024 and ending in 2034.

9. Subject Population

Describe the characteristics of the proposed subject population.

Include:

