1. Total number of participants to be studied
2. Age
3. Gender
4. Ethnic background
5. Health status

State the inclusion and exclusion criteria for participants to be enrolled on this study.

Indicate whether any vulnerable groups such as children, pregnant women, prisoners, adults unable to consent will be included and provide rationale for involving such participants.

We anticipate enrolling 25-60 donors. Study participation will not be limited to donors of any specific race or ethnic background.

June 2024 Amendment: Only donors who received the late-season 23-24 vaccine will be eligible to continue and receive the 2024-25 vaccine in Sep-Nov, since we only want participants who had been given a late-season influenza vaccine.

Inclusion Criteria

All of the donors will correspond to the following criteria:

- Be between 18-64 years of age
- Males or non-pregnant, non-nursing females
- Weigh at least 85 pounds for whole blood draw
- Ability to provide signed informed consent
- Subjects must plan to receive the intramuscular influenza vaccine at LJI

Vaccinated at LJI:

All subjects will receive the approved intramuscular quadrivalent Fluzone influenza vaccine for the 2023 season at LJI. Enrollment will begin in May, and subjects will receive their vaccine before its expiration date at the end of June 2024. Every year the LJI clinical core offers a seasonal influenza vaccination program for LJI employees, the Clinical Core licensed nursing staff are trained in administering these vaccines. All vaccinations are administered under current standing orders on file by the LJI Medical Director, [name].

June 2024 Amendment: All subjects will now receive the approved intramuscular quadrivalent Fluzone influenza vaccine for the **2024 season** at LJI. These vaccines will be administered before December 2024.

Exclusion Criteria:

All of the donors will correspond to the following criteria:

- Received an influenza vaccine in the past year
- HIV, HBV, HCV infection
- History of certain anemias
- Presence of significant cardiovascular disease, systemic diseases including, but not limited to, diabetes which is not controlled, renal disease, liver disease, malignancy, infection, or blood clotting disorder
- Inability to provide informed consent
- Recent whole blood donation within 56 days or leukapheresis within 112 days
- Children (under 18 years of age), elderly (65 years of age or older), pregnant or nursing females
- Individuals with egg allergies

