A potential subject will be verbally consented by LJI Coordinators to take part in an initial telephone or in person screening questionnaire (see attached). If the donor meets all eligibility criteria, they will be consented to enroll into the study. The enrollment consent will be obtained via the phone or over email. All subjects will be given as much time as needed to review the consent form and ask any questions they may have regarding the study. This is described in more detail below in Section 19 (Informed Consent). As described in the Informed Consent, participants can withdraw from the study at any point.

The study is designed such that we will capture participants pre-vaccination, at their peak-immune response (day 28), and at a longer-term time point to assess durability (day 90). Once informed consent is obtained, we will obtain a blood draw (20 mL) at each time point. After their first blood draw at day 0, each participant will be given the 2023 influenza FluZone vaccine.

The anticipated time points are:

- May/Jun 2024, Day 0 after the first vaccination: **Vaccination** and 20 mL blood draw
- Jul 2024, Day 28 after the first vaccination: 20 mL blood draw
- Sep 2024, Day 90 after the first vaccination: 20 mL blood draw
- Sep-Nov 2024, Day 0 after the second vaccination: **Vaccination** and 20 mL blood draw
- Dec 2024, Day 28 after the second vaccination: 20 mL blood draw

Feb 2025, Day 90 after the second vaccination: 20 mL blood draw

Influenza vaccines typically become available in September or October, and we will administer them as soon as they are purchased. The range (Sep-Nov) of the second vaccination date will ensure that the second round of vaccines will be available and help accommodate any schedule conflicts for participants.

We will try to adhere to this schedule, but we expect that not all participants will return at exactly day 28 or day 90 after either vaccination, and we will mark down their exact dates for their post-vaccination visits. Deviations by as much as 2 weeks are acceptable, since the antibody response is known to peak around day 7-14 and then stays at this maximal level for at least 1 month.

Institutional Review Board

Human Subjects Protocol Narrative

Human subjects protocol narrative – Version 2.1 August 17th 2021

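### Aim 4's contrast with fall-2023 vaccinees can show whether late timing beats standard timing, but cannot by itself show that the late dose primes or boosts the 2024 response

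*Protocol*

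**What the plan says.** The aim is stated in absolute and in comparative terms.

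- **Absolute.** Section 6, Aim 4 opens: "Does administering the 2023 vaccine late in the season prime the subsequent 2024 response". The section 7 amendment closes: "Our goal will be to demonstrate whether such late-season vaccine administration can boost subsequent vaccine responses".
- **Comparative.** The second sentence of Aim 4 sets the cohort against "responses from other influenza vaccine studies (where participants are annually vaccinated") and asks whether the regime gives stronger or more durable responses. The section 3 amendment asks "whether the late-season 2023 vaccine primed this cohort to respond better to the standard 2024 vaccine", given at standard timing.

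The comparator is fixed in the section 7 amendment: people receiving the 2024 vaccine "whose previous vaccine was either administered: (1) in May/June [our late-season vaccine study] or (2) in the Fall of 2023".

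Two eligibility rules define the cohort. Section 9 excludes anyone who "Received an influenza vaccine in the past year", and the section 10 pre-screening questions exclude anyone vaccinated in 2023-2024. For the second dose, section 9 states: "Only donors who received the late-season 23-24 vaccine will be eligible to continue and receive the 2024-25 vaccine in Sep-Nov".

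**The concern.** To say that a dose primed or boosted a later response is to compare with the same people not given that dose. The eligibility rules make clear what that would mean here: without the study dose, and absent vaccination elsewhere, participants would have reached fall 2024 with no 2023-24 dose. The named comparator is in a different state, because it had a 2023-24 dose in fall 2023. There is no internal substitute either, since everyone who continues to the second dose has had the late one.

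At stake is which conclusion the Aim 4 result can carry. The gap lies in what is estimated, not in precision, so no enrolment within the planned 25-60 closes it.

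**Working it through.** The protocol gives no effect size, standard deviation or test for Aim 4, so there is no stated figure to reproduce. The check is algebra with assumed values.

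**1. What differs between the groups.** The cohort is dosed in May/June 2024 and again at "Sep-Nov 2024, Day 0 after the second vaccination" (section 11). For fall 2023, I take the September-November window that section 6 gives under Aim 2. I assume the same window for the comparators' 2024 dose. The interval from the earlier dose to the 2024 dose, at 30.4375 days per month, is:

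- Late cohort: 30 June to 1 September 2024 is 63 days, or 2.1 months; 1 May to 30 November 2024 is 213 days, or 7.0 months.
- Fall-2023 recipients: 30 November 2023 to 1 September 2024 is 276 days, or 9.1 months; 1 September 2023 to 30 November 2024 is 456 days, or 15.0 months.

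So the contrast is about 2-7 months against about 9-15 months since the earlier dose. If the day-90 visit comes before the second dose, the lower limit for the cohort is about 3 months. This is a contrast of timing. Neither group lacks an earlier dose.

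**2. What the contrast estimates.** Let U be the expected response to the 2024 vaccine with no 2023-24 dose. Let p_late and p_fall be the multiplicative effects of an earlier dose at each time. Suppose the groups are otherwise comparable, which favours the plan.

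- Planned contrast: (p_late × U) / (p_fall × U) = p_late / p_fall
- Priming by the late dose: (p_late × U) / U = p_late

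The two agree only when p_fall = 1.

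**3. Range over p_fall (assumed values).**

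| p_late | p_fall | Planned contrast | Priming | Reading |
|---|---|---|---|---|
| 2 | 2.83 | 0.71 | 2 | reversed |
| 2 | 2 | 1.00 | 2 | hidden |
| 2 | 1.41 | 1.41 | 2 | understated |
| 2 | 1 | 2.00 | 2 | correct |
| 2 | 0.5 | 4.00 | 2 | overstated |
| 1.5 | 2 | 0.75 | 1.5 | reversed |
| 1 | 0.5 | 2.00 | 1 | apparent priming where there is none |

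**4. What the documents say about p_fall.** Section 14 says that antibody stays raised for at least a year after vaccination in healthy adults. This makes it unsafe to assume that the fall-2023 dose has no remaining influence. It gives neither the direction nor the size of any effect on the response to the next vaccine.

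**5. With the missing comparator.** Against 2024-vaccine recipients with no 2023-24 dose, the contrast is p_late itself: 2.00 in the first five rows, 1.5 in the sixth and 1 in the last, whatever p_fall is.

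**The case against.** The strongest reply is that Aim 4 explains itself. Its second sentence names annually vaccinated people as the comparator and asks about relative strength and duration; the section 3 wording is also comparative. On that reading the fall-2023 group is the right one. This stands. A reader might infer that the design cannot answer Aim 4 at all, and the documents do not support that.

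A reader might also infer that a null result will be reported as an absence of priming, or that masking is the expected outcome. The protocol has no decision rule for Aim 4 and names its comparator openly, so the first is conjecture. The second holds only if p_fall is above 1. Near 1 the difficulty disappears, and below 1 the error runs the other way.

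Finally, useful data may already be in view. The third group in section 7, future studies giving the 2024 vaccine, is not restricted by vaccination history, and the cohort's own first-dose response comes from people unvaccinated in the previous year. But neither is assigned to Aim 4, and the first-dose response is to the 2023 formulation.

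What remains is that the absolute wording in the opening of Aim 4 and in the section 7 goal goes beyond what the named comparator can show.

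**Conclusion.** The point holds in limited form. The planned contrast is a valid late-versus-fall timing comparison, subject to its being external and non-randomised. It does not by itself support a conclusion that the late dose primes or can boost the 2024 response, because it estimates p_late/p_fall while those words refer to p_late. The discrepancy is a factor of 1/p_fall. For a true 2-fold effect, values of p_fall from 2.83 down to 0.5 give contrasts from 0.71 to 4.00.

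This rests on two readings of the text: that fall-2023 recipients had that season's formulation (the external brand is not stated), and that participants would otherwise have had no 2023-24 dose. All values of p are illustrative, so neither the direction nor the size of the actual discrepancy is known. The algebra also sets aside differences in vaccination habit: the cohort had no influenza vaccine in the year before enrolment, while the comparators are annual vaccinees.

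**What to change.** In the section 7 amendment:

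1. Keep the cohort against fall-2023 recipients, and label it the late-versus-standard-timing contrast.
2. Where external fall-2024 studies record vaccination history, add a contrast with 2024-vaccine recipients who had no 2023-24 dose. Make this the basis for any conclusion about priming or boosting.
3. If such records cannot be obtained, restrict the Aim 4 question in section 6, the section 3 amendment and the section 7 goal to late versus fall timing, and drop priming and boosting as conclusions.

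The cost is protocol wording and the selection of external records by vaccination history. No new participants or visits are needed. The added group would also match the cohort in having no fall-2023 dose, which annual vaccinees do not. The drawback is that such people may be few in studies of annual vaccinees, so the interval will be wider, and the comparison remains external and non-randomised.
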